4.4.2.2 PRO Secondary Endpoints

The PRO secondary endpoints are listed below:

- Change from baseline at Week 52 in UCSD-SOBQ score
- Change from baseline at Week 52 in SGRQ total score

The PRO secondary endpoints will be analyzed using the same estimand strategy, descriptive statistics and model as Hgb-corrected DL_{CO} % predicted in Section 4.4.2.1 and will be analyzed at a 0.05 two-sided significance level.

4.4.2.3 Time-to-Event Secondary Endpoints

The time-to-event secondary endpoints are listed below:

- Time to disease progression, defined as time to first occurrence of $\geq 10\%$ absolute decline in % predicted FVC, $\geq 15\%$ relative decline in 6MWD, or death
- Time to first respiratory-related hospitalizations (defined as non-elective hospitalizations due to any respiratory cause, including acute exacerbations of IPF, or suspected acute exacerbations of IPF, as determined by the Clinical Adjudication Committee)
- Time to first acute exacerbation of IPF, or suspected acute exacerbation of IPF, as determined by the Clinical Adjudication Committee
- Survival, as measured by all-cause mortality

Descriptive statistics for the frequency of each type of event will be provided. The stratified log rank test (on stratification factors) will be used to compare the time to event endpoints between two treatment arms at a 0.05 two-sided significance level. The Kaplan-Meier plot, median time to event, and their 95% CIs, and a p-value from the log-rank test will be presented. The hazard ratio and its 95% CI will be estimated using a Cox proportional hazards model, adjusting for sex, age, and height. In fitting the Cox model, ties will be handled with the approximate likelihood method of Efron (1977).

Time-to-event will be measured in reference to Baseline Day 1 through the end of study. Patients are considered to be in the placebo-controlled period even if they have discontinued study treatment, if they would still be receiving placebo-controlled study treatment had they not discontinued. For time to first respiratory-related hospitalizations and time to first acute exacerbation of IPF, patients not experiencing an event will be censored at the earliest of the last day known alive, or the last date during the placebo-controlled period (see Section 1.2). For disease progression and survival (all-cause mortality), patients without an event will be censored at the last clinic assessment during the placebo-controlled period.

The estimand strategy for the time-to-event endpoints are summarized below in Table 7.

**Table 7 Estimand Analysis Strategy for Intercurrent Events:
Time-to-Event Secondary Endpoints**

Endpoints	Estimand

 Time to disease progression, defined as time to first occurrence of $\geq 10\%$ absolute decline in % predicted FVC, $\geq 15\%$ relative decline in 6MWD, or death 	
Population: see primary endpoint Treatment: see primary endpoint Population-level summary measure: log rank test and hazard ratio Intercurrent events:
 
 Any patients who undergo lung transplantation will be censored at the date of the transplant (hypothetical strategy)

 Survival, as measured by all-cause mortality 	
Population: see primary endpoint Treatment: see primary endpoint Population-level summary measure: log rank test and hazard ratio Intercurrent events:
 
 Any patients who undergo lung transplantation will be censored at the date of the transplantation (hypothetical strategy)

 Time to first respiratory-related hospitalizations (defined as non-elective hospitalizations due to any respiratory cause, including acute exacerbations of IPF, or suspected acute exacerbations of IPF, as determined by the Clinical Adjudication Committee) 	
Population: see primary endpoint Treatment: see primary endpoint Population-level summary measure: log rank test and hazard ratio Intercurrent events:
 
 Deaths are expected to be infrequent, but in case of occurrence, they will be treated as disease progression and counted as event of interest (composite strategy) Any patients who undergo lung transplantation will be censored at the date of the transplantation (hypothetical strategy)

 Time to first acute exacerbation of IPF, or suspected acute exacerbation of IPF, as determined by the Clinical Adjudication Committee 	
Population: see primary endpoint Treatment: see primary endpoint Population-level summary measure: log rank test and hazard ratio Intercurrent events:
 
 Deaths are expected to be infrequent, but in case of occurrence, they will be treated as disease progression and counted as event of interest (composite strategy) Any patients who undergo lung transplantation will be censored at the date of the transplantation (hypothetical strategy)

6MWD = 6-minute walk distance; FVC = forced vital capacity; IPF = idiopathic pulmonary fibrosis.

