6.5.4 Other Secondary Efficacy Analyses

As mentioned in Section 6.5, and conditional to significant results being obtained first on the primary endpoint and then the key secondary endpoint, the remaining secondary endpoints will be tested using the fixed-sequence strategy in the predefined order presented in Section 2.1.2, each at the same significance level of 0.05 two-sided and the testing sequence will stop as soon as a non-significant result is observed.

In case a non-significant test occurs during this testing sequence, the tests for the remaining endpoints in the sequence will nevertheless be computed as sensitivity/exploratory analyses but will not allow any formal claim of efficacy on these endpoints.

All continuous secondary endpoints will be analyzed using the same methodology as the primary endpoint. The SAP will detail specifics for models and summaries.

For time to event endpoints, the log-rank test will be used for the comparison between the two treatment arms. The hazard ratio will be estimated using a Cox regression model. Descriptive statistics and Kaplan-Meier curves will be provided. Details on model specifications will be provided in the SAP.

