4.3.3 Sensitivity Analyses for Primary Endpoint

4.3.3.1 Sensitivity Analysis Addressing the Effect of Missing Data After Death due to IPF

To analyze the effect of missing data after death, a rank analysis of covariance (ANCOVA) model will be fit, where patients who die are assigned the worst rank. Specifically, for each patient who survives the duration of the trial, a slope will be calculated from a line fit through their observed FVC assessments. The slopes will then be ranked, assigning the worst rank to patients who die. The rank ANCOVA model will include age, sex, height and ranked baseline score as covariates.

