4.3.3.1.1 Sensitivity Analysis Addressing the Effect of Missing Data After Treatment Discontinuation

Patients are expected to continue with study assessments after permanent treatment discontinuation. However, it is possible that patients who discontinue treatment fail to return for their follow-up assessments or discontinue the study, in which case some post-discontinuation data would be missing. Analysis under MAR will implicitly impute these missing values based on all observed data without distinguishing between on-treatment and off-treatment data and may therefore overestimate the treatment effect. Furthermore, the ICE strategy for treatment discontinuation would be a hybrid between a hypothetical and treatment policy strategy, and it becomes unclear what treatment effect is actually being estimated.

More conservative imputation approaches will be implemented to assess the sensitivity of treatment effect estimation and inference to missing data assumptions. The first approach will be to use conditional mean imputation for reference-based imputation of missing data ([Wolbers et al. 2022](#)). The imputation model will be an MMRM with baseline outcome, age, sex, height, treatment group, visit and treatment-by-visit interactions as covariates. Missing data for patients in the placebo arm will be imputed under MAR, and missing data for patients in the zinpentraxin alfa arm will be imputed under copy increments in reference. Under this reference-based assumption, patients in the intervention arm who discontinue treatment do not get any further benefit from treatment after discontinuation. The imputed, complete data will be analyzed via ANCOVA, with FVC (mL) slope as the outcome and baseline FVC, age, sex, height and treatment as covariates. Re-sampling based inference for the treatment effect estimate will be obtained via the jackknife.

In addition to the reference-based imputation, a tipping point analysis will be implemented by applying different delta-adjustments for each treatment group to the imputed data to see which combination of delta values tip the primary analysis result.

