4.3.3.1.2 Sensitivity Analysis Addressing Non-linearity

To evaluate the impact of assuming a linear disease trajectory, a repeated measures mixed-effects model (MMRM) will be used to estimate the difference in mean change from baseline in FVC (mL) at Week 52. For this sensitivity analysis, only data from scheduled assessments will be used to fit the MMRM. The response variable for the model is change from baseline in FVC (mL). The following variables will be included as model terms: baseline FVC (mL), stratification factors, treatment group, visit and treatment-by-visit interaction. Subject, treatment, and visit will be class variables and the within-subject errors will be assumed to have an unstructured variance-covariance matrix. If the analysis fails to converge, the following covariance structures will be tested: compound symmetry, first-order autoregressive [AR(1)], and Toeplitz. The covariance structure converging to the best fit, based on Akaike's information criterion (AIC), will be used.

The difference in the least squares mean change from baseline between the zinpentraxin alfa and placebo groups will be estimated at each post-baseline visit, as well as 95% CI's and p-values. The MMRM LS means plot with CI's will be made to visualize the estimates.

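### Time-to-event p-values use a log-rank test stratified on the randomisation factors, but the hazard ratio and its interval come from a Cox model that lists neither factor; three sensitivity models omit them too

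*SAP*

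**What the plan says.** SAP 4.4.2.3 gives the test first: "The stratified log rank test (on stratification factors) will be used to compare the time to event endpoints between two treatment arms". For the estimate it then says: "The hazard ratio and its 95% CI will be estimated using a Cox proportional hazards model, adjusting for sex, age, and height". It does not say that the Cox model is stratified. Table 7 gives the same entry for each of the four endpoints, "Population-level summary measure: log rank test and hazard ratio", without saying whether the hazard ratio is conditional on strata. Protocol 6.5.4 does not settle it: "Details on model specifications will be provided in the SAP". SAP Appendix 1 gives no reason for the difference. SAP 4.5 carries the same methods over to the exploratory time-to-event endpoints.

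Two sensitivity analyses of the primary endpoint leave the factors out as well. For death (SAP 4.3.3.1): "The rank ANCOVA model will include age, sex, height and ranked baseline score as covariates". For treatment discontinuation (SAP 4.3.3.1.1): "The imputation model will be an MMRM with baseline outcome, age, sex, height, treatment group, visit and treatment-by-visit interactions as covariates". The completed data then go to an ANCOVA "with FVC (mL) slope as the outcome and baseline FVC, age, sex, height and treatment as covariates". By contrast, the primary model in SAP 4.3.2 contains both factors, and the non-linearity MMRM in SAP 4.3.3.1.2 lists "baseline FVC (mL), stratification factors, treatment group, visit and treatment-by-visit interaction".

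**The concern.** The test and the interval for one endpoint should describe the same comparison. Here the test compares arms within randomisation strata without covariates, while the hazard ratio adjusts for three demographic variables and pools over strata. A p-value below 0.05 could be printed beside an interval that includes 1, or the reverse. If the factors predict outcome, the pooled hazard ratio is also drawn toward 1 and its interval becomes conservative. These endpoints stand third, fourth, seventh and ninth in the secondary sequence, so a contradictory pair could land on a formal claim.

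The sensitivity analyses exist to isolate one missing-data assumption. Changing the adjustment set at the same time mixes a second difference into the comparison with the primary result.

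**Working it through.** **The plan's own figure.** SAP 2.2.1 states power 0.89 for the primary endpoint with 329 per arm, standardised effect 0.25 and two-sided alpha 0.05. Φ(0.25 × √(329/2) − 1.96) = Φ(3.206 − 1.960) = Φ(1.246) = 0.894, so it reproduces. The SAP states no event rate, hazard ratio or power for the time-to-event endpoints. The sizes below therefore rest on assumed inputs.

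**Step 1: what each model contains.**

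| Analysis (SAP section) | Randomisation factors | Age, sex, height |
|---|---|---|
| Primary model (4.3.2) | yes | yes |
| Rank ANCOVA, death (4.3.3.1) | no | yes |
| Imputation MMRM and slope ANCOVA (4.3.3.1.1) | no | yes |
| Non-linearity MMRM (4.3.3.1.2) | yes | no |
| DLCO and PRO MMRM (4.4.2.1, 4.4.2.2) | yes | no |
| Log-rank test (4.4.2.3) | yes, as strata | no |
| Cox model (4.4.2.3) | not listed | yes |

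**Step 2: first simulation of test against interval.** From the documents: 658 patients, 1:1 permuted blocks, 3 × 5 = 15 strata. Assumed: block size 4, 12% loss per year, an unmodelled severity covariate (log hazard ratio 0.4 per SD), hazard ratio 0.55 with 10% events (about 65) or 0.77 with 55% events (0.55 × 658 ≈ 362), and 4,000 trials per scenario. Disagreement means that the log-rank p-value and the 95% CI fall on opposite sides of 0.05.

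| Factor effect on log hazard, per factor | 0 | ±0.3 | ±0.6 |
|---|---|---|---|
| Planned Cox, about 65 events | 2.9% | 3.9% | 4.2% |
| Planned Cox, about 362 events | 5.1% | 6.4% | 11.8% |

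- Cox stratified on the same factors, treatment only: 0.7 to 0.9% (about 65 events) and 0.0 to 0.2% (about 362).
- Stratified Cox keeping sex, age and height: 2.7 to 4.8%.
- Stratified Cox with age and severity: 5.0 to 11.4%.
- The mean hazard ratio differs between the planned and stratified models by at most 0.005, except with strong factors and many events (0.801 planned, 0.782 stratified).
- Log-rank rejection rate with no treatment effect: 4.7%.

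**Step 3: second simulation, different assumptions.** 658 patients, 2,000 runs per scenario, 12% dropout, hazard ratio 0.7 or 1.0, with no, moderate or strong factor effect. Disagreement at hazard ratio 0.7 (none / moderate / strong):

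| 52-week risk | Planned Cox | Stratified, with sex, age, height | Stratified, treatment only |
|---|---|---|---|
| 5% | 1.8 / 2.6 / 3.7% | 2.1 / 2.2 / 3.3% | 1.6 / 1.1 / 1.1% |
| 10% | 2.1 / 4.0 / 8.7% | 1.8 / 3.6 / 5.7% | 0.6 / 0.5 / 0.7% |
| 35% | 3.4 / 7.1 / 17.9% | 1.9 / 5.8 / 5.4% | 0.2 / 0.4 / 0.1% |

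At 35% risk the planned model's median hazard ratio was 0.700 / 0.710 / 0.753, against 0.700 / 0.702 / 0.706 for the treatment-only stratified model. With no treatment effect, the planned model disagreed with the test in 0.7 to 3.8% of runs and the treatment-only stratified model in 0.0 to 0.6%. At 35% risk and no treatment effect, the planned interval excluded 1 in 4.3 / 3.7 / 1.9% of runs, against 4.2 / 4.9 / 5.1% rejection by the log-rank test. Stratifying changed the median standard error of the log hazard ratio by about 0 to 2%.

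A further run of 800 trials per scenario gave about 3 to 4% disagreement with about 70 events and 7 to 11% with about 355. The treatment-only stratified model stayed under 1%.

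**Step 4: sensitivity models.** Rank ANCOVA: SD 403.5 mL (SAP 2.2.1); assumed effect 85 mL, 5% deaths ranked worst, 4,000 trials per setting.

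| Factor effect (mL per year) | SE reduction from adding factors | Power without → with | Significance changes |
|---|---|---|---|
| ±50 | 0.6% | 64.3 → 64.7% | 0.6% of trials |
| ±100 | 2.3% | 61.9 → 63.9% | 2.2% |
| ±150 | 5.0% | 60.3 → 64.1% | 3.9% |

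Reference-based imputation (250 trials per setting, 17% dropout depending on stratum): the mean shift was at most 0.1 mL. In 95% of trials the estimates with and without the factors differed by no more than 1.1 to 2.8 mL, for an effect of about 75 mL.

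**Step 5: sparse cells.** 658 / 15 ≈ 44 patients per cell on average. With the shares assumed in step 2, the smallest cell holds about 14 patients, which is 14 × 0.10 ≈ 1 to 2 events at a 10% event rate.

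**The case against.** The strongest reply is that missing strata are not the main cause. With zero factor effect the planned model already disagrees with the test in 2.9% of trials at about 65 events, and stratifying while keeping sex, age and height still leaves 2.7 to 4.8%. At low event counts the covariates do most of the work. This is correct, and it is why the remedy has to be a treatment-only stratified model.

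Second, a stratified test beside a covariate-adjusted hazard ratio is a legitimate prespecified pair, and the remedy changes which hazard ratio is reported. That is true, but the adjusted estimate can stay as supportive. A pooling order would touch the confirmatory test, but the planned log-rank test already faces the same sparse cells.

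Third, the sizes depend on assumptions. The chosen effects give moderate power, where two similar tests easily straddle 0.05, and ±0.6 on both factors implies about an 11-fold hazard range between extreme cells (exp 2.4). This stands: the upper figures are strong cases.

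Fourth, the SAP varies its covariates elsewhere, and the primary model's non-convergence rule drops the factors before age, sex and height. That rule is a fallback for a model that will not fit. It does not explain leaving the factors out of an ANCOVA from the start. For the imputation analysis, though, the effect is indeed negligible.

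Finally, the lack of stratification is inferred from what the SAP does not list. If stratification was intended, one sentence settles it.

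**Conclusion.** The concern holds. As written, the test and the interval for all four time-to-event secondary endpoints come from different models, and nothing else in either document reconciles them. This is a defect of consistency and reporting. Type I error is intact, because the stratified log-rank test governs the fixed sequence.

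The size depends on inputs the documents do not give. With few events, contradictory results appear in a few per cent of trials. With many events and prognostic factors the rate reaches 11.8% in one simulation and 17.9% in another, and the hazard ratio moves toward 1. A treatment-only stratified Cox model keeps disagreement at 1.6% or below in every scenario run.

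The sensitivity-model omission is smaller: 0.4 to 3.8 points of power in the rank ANCOVA, and no bias in the imputation analysis. Adding the factors removes one avoidable difference from the primary model. It does not make these analyses directly comparable with it, because they also change the outcome scale to ranks or per-patient slopes.

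**What to change.** Before unblinding, amend the SAP as follows.

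1. In 4.4.2.3, take the main hazard ratio and 95% CI from a Cox model with treatment as the only covariate, stratified on the same two factors as the log-rank test. State one pooling order for sparse cells and use it in both.
2. Report any covariate-adjusted hazard ratio as supportive only, whether with sex, age and height as now planned, or with age, baseline FVC% predicted and 6MWD.
3. Add both stratification factors to the rank ANCOVA (4.3.3.1) and to the imputation MMRM and slope ANCOVA (4.3.3.1.1).

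The cost is SAP wording, with no extra patients, data or alpha. The statistical price is close to nil: about 2% at most on the standard error of the log hazard ratio in the simulations, and (3 − 1) + (5 − 1) = 6 parameters for additive factor terms in each sensitivity model.

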- Concurrent use of nintedanib treatment versus pirfenidone treatment versus no concurrent treatment
- Region: China (including Hong Kong and Taiwan), North America (United States and Canada), Europe (including eastern Europe), Latin America, and Rest of World (including east Asia, Australia, and New Zealand)

All patients will have a final assessment visit at Week 52 (4 weeks after the final study drug infusion). Patients will be invited to enroll in an OLE study at this point (Study WA42294), and if they roll over into that study, the Week 52 visit will be considered their end of study visit. Patients who do not enroll in the OLE study will have their end of study visit at Week 56, in addition to the Week 52 visit (see [Table 1](#)).

Table 1 Final Assessment and End of Study Visits

	Last Infusion of Study Treatment	Final Assessment Visit	End of Study Visit
Patients enrolling in OLE study for ongoing PRM-151 treatment	Week 48	Week 52	Week 52
Patients enrolling in OLE study for survival follow-up only	Week 48	Week 52	Week 56
Patients not enrolling in OLE study	Week 48	Week 52	Week 56

OLE = open-label extension study (Study WA42294).

This study will enroll approximately 658 patients globally across all sites. Enrollment will be globally competitive. After completion of the global enrollment phase, additional patients may be enrolled in an extended China enrollment phase at sites in mainland China, Hong Kong, and Taiwan. The global population will include all patients enrolled during the global enrollment phase and the China subpopulation will include all patients *enrolled in China, Hong Kong, and Taiwan* (i.e., during both the global enrollment phase and the extended China enrollment phase).

Individuals who do not meet the criteria for participation in this study (screen failure) may be eligible for rescreening once for selected reasons. In addition, the screening period may be extended if a patient fails a test due to technical issues with the test and the patient will be allowed to repeat the test (e.g., lab sample hemolyzed and not able to be analyzed).

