5.4.1 Adverse Event Reporting Period

Investigators will seek information on adverse events at each patient contact. All adverse events, whether reported by the patient or noted by study personnel, will be recorded in the patient's medical record and on the Adverse Event eCRF.

After informed consent has been obtained but prior to initiation of study drug, only serious adverse events caused by a protocol-mandated intervention (e.g., invasive procedures such as biopsies, discontinuation of medications) should be reported (see Section 5.5.2 for instructions for reporting serious adverse events). *All other medical occurrences that begin before the start of study treatment but after obtaining informed consent will be recorded on the General Medical History and Baseline Conditions eCRF, and not on the Adverse Event eCRF.*

After initiation of study drug, all adverse events will be reported until 8 weeks after the final dose of study drug.

Instructions for reporting adverse events that occur after the adverse event reporting period are provided in Section 5.7.

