1.2 STUDY DESIGN

Study WA42293 is a Phase III, randomized, double-blind, placebo-controlled, pivotal clinical trial designed to confirm the efficacy and safety of zinpentraxin alfa in the treatment of IPF patients with or without concurrent treatment with pirfenidone or nintedanib.

Approximately 658 patients will be randomly assigned on a 1:1 basis to treatment with zinpentraxin alfa at a dose of 10 mg/kg or matched placebo on Days 1, 3, and 5, then one infusion every 4 weeks (Q4W) for 48 weeks. Patients will be evaluated for study eligibility during a screening period of up to 4 weeks. Study treatment will be administered by intravenous (IV) infusion over 50–70 minutes every 4 weeks. If any infusions are missed, repeat loading doses will be required at the next scheduled visit (three doses administered on alternate days). During the placebo-controlled treatment period (defined as Day 1 to Week 52), patients will continue to receive blinded study treatment every 4 weeks to Week 48 and have a final assessment visit at Week 52.

[figure not shown]
This study will enroll approximately 658 patients globally across all sites. Enrollment will be globally competitive. After completion of the global enrollment phase, additional patients may be enrolled in an extended China enrollment phase at sites in mainland China, Hong Kong, and Taiwan. The global population will include all patients enrolled during the global enrollment phase and the China subpopulation will include all patients enrolled at sites in mainland China, Hong Kong, and Taiwan (i.e., during both the global

enrollment phase and the extended China enrollment phase). Separate analyses will be performed for the global population and the China subpopulation (see Section 4.7.6 for China subpopulation analyses).

Following participation in this study, patients may be eligible to participate in a separate open-label extension (OLE) study (Study WA42294) to receive treatment with zinpentraxin alfa and further study assessments. Patients who do not enroll in the OLE study will be followed up for an additional 4 weeks (to Week 56, for safety monitoring). The OLE study will also consist of a long-term survival cohort, where patients who do not want further study assessments or treatment can enroll (for long-term collection of survival data only).

The study schema is shown in Figure 1.

Figure 1 Study Schema

IV=intravenous; OLE=open-label extension; Q4W=once every 4 weeks.

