^a Patients will have a final assessment visit at Week 52 (4 weeks after the final study drug infusion). For patients enrolling into the OLE study, this will also be their end of study visit.

^b Patients who do not enroll in the OLE study will have their final assessment visit at Week 52, followed by an end of study visit at Week 56 (8 weeks after the final study drug infusion).

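### Time-to-event endpoints count events to the end of study (Week 56 for some patients) but censor event-free patients by Week 52, so the Kaplan-Meier tail and median can be false

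*SAP*

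**What the plan says.** SAP 4.4.2.3 sets the counting window for all four time-to-event endpoints: "Time-to-event will be measured in reference to Baseline Day 1 through the end of study".

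The same paragraph sets the censoring. For respiratory hospitalisation and acute exacerbation, patients without an event are "censored at the earliest of the last day known alive, or the last date during the placebo-controlled period". For disease progression and survival, "patients without an event will be censored at the last clinic assessment during the placebo-controlled period". SAP 1.2 defines the placebo-controlled period as Day 1 to Week 52.

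End of study is not the same date for everyone. Protocol Table 1 (section 3.1.1) puts it at Week 52 for patients continuing on drug in the extension. It is Week 56 for patients who do not enrol and for those listed as "Patients enrolling in OLE study for survival follow-up only". Footnote b to the SAP study schema also gives Week 56 for patients not enrolling.

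Events in those last four weeks are collected. Under Protocol 5.4.1, once study drug has started, "all adverse events will be reported until 8 weeks after the final dose of study drug", which is Week 56 for a patient last dosed at Week 48.

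For each endpoint the SAP will present the Kaplan-Meier plot, the median with its 95% CI, a stratified log-rank p-value and a Cox hazard ratio.

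**The concern.** A Kaplan-Meier estimate needs events and event-free follow-up to be observed over the same window. Here the text lets an event count up to Week 56 but takes event-free patients out of the risk set by about Week 52. Beyond that point the only patients still at risk are those who will themselves have a late event, so the curve must step down to zero.

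The consequence would be visible in the report. An arm with about 90% of patients event-free at Week 52 could be shown falling to zero with a median of about 54 weeks, next to an arm whose median is not reached. The log-rank p-value would not reflect any such contrast. Whether a late event can count at all would also depend on the patient's choice at Week 52 about the extension, a decision made after randomisation.

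**Working it through.** **The plan's own figure.** The documents give no event count, rate or power for any time-to-event endpoint. The only stated figure in play is the arm size. With 329 per arm and standardised effect 0.25, √(329/2) × 0.25 = 3.21, and Φ(3.21 − 1.96) = 0.89, which matches the stated power. So 329 per arm is used below.

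**One arm, by hand.** Assume 33 events (10%) before Week 52 and event-free patients censored at Day 364.

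- At Week 52: S = (329 − 33)/329 = 296/329 = 0.900.
- One late event at Day 380, one patient at risk: 0.900 × (1 − 1/1) = 0. Reported median: Day 380.
- Two late events: 0.900 × 1/2 = 0.450, then 0. The median is the first late event.
- Three late events: 0.900 × 2/3 = 0.600, × 1/2 = 0.300, then 0. The median is the second late event.
- Events and censoring both stopped at Week 52: the curve ends at 0.900 and the median is not reached.

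**How often.** Assume a constant hazard, 52-week event rate r, and a share s of patients followed to Week 56. The chance of an event in the four weeks after Week 52 is p = 1 − (1 − r)^(4/52). About n = 329(1 − r)s event-free patients per arm could have such an event. If all censoring is exactly at Week 52, any late event produces a false median, so P(at least one arm) = 1 − (1 − p)^(2n).

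For r = 10% and s = 10%: p = 0.0081, n = 29.6, P = 0.38. For r = 10% and s = 30%: n = 88.8, P = 0.76 (0.75 by simulation).

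The protocol's schedule of activities allows visits within ±5 days, and ±2 weeks after early drug discontinuation, so some event-free patients stay at risk past Day 364. Simulating this with 15% early discontinuers (an assumption) gives lower figures:

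| 52-week event rate | Censoring exactly at Week 52 | With visit windows |
|---|---|---|
| 5% | 22–52% | about 13–32% |
| 10% | 38–75% | about 21–55% |
| 15% | 50–88% | about 31–70% |

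Each range runs from s = 10% to s = 30%.

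**Effect on the test.** A late event with one patient at risk adds nothing to the log-rank statistic or the Cox partial likelihood. In 4,000 simulated null trials (r = 10%, s = 20%, ±5-day visits, unstratified log-rank), the mean absolute change in z against a common Week 52 cut-off was 0.03. Type I error was 0.052 under the rule as written and 0.054 with the common cut-off.

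**The case against.** The strongest reply is that the paragraph is about the placebo-controlled period and one phrase in it is loose. Protocol 3.1.1 speaks of a 52-week study period and describes the follow-up to Week 56 as safety monitoring. Final efficacy assessments are at Week 52, and both censoring rules refer to the placebo-controlled period. The sponsor may well have meant Week 52 throughout.

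That may be the intention, but no sentence says it. SAP 4.6 treats the entire study period as the placebo-controlled period plus safety follow-up for patients not entering the extension, so the SAP distinguishes the two. Protocol 3.2 defines the end of the study as last patient, last visit or later, which is also after Week 52. SAP section 4 runs the primary analysis after the last global patient has completed the study, so late events will be in the database. A programmer following the text would count them.

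Other parts of the reply stand:

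- SAP Table 7 names the log-rank test and hazard ratio as the summary measures, and these are nearly unaffected. A reader might infer that the confirmatory tests are compromised; the calculation does not support that.
- A reader might also infer that any late event sends the curve to zero. That requires the event to fall after the arm's last event-free censoring time. Within the visit windows, an earlier late event gives a large drop instead.
- Nor does the problem apply equally to all four endpoints. Disease progression has its last FVC and walk-distance assessments at Week 52, so its late events would be mostly deaths, and it may reach a genuine median earlier.
- Adverse-event reporting ends before Week 56 for patients who stopped drug early, which limits the number of late events somewhat.

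**Conclusion.** Wrong as written, minor to moderate. The counting window and the censoring window in SAP 4.4.2.3 end at different dates for patients who do not continue on drug. Followed literally, this can produce a false Kaplan-Meier tail and a false median with its CI, mainly for respiratory hospitalisation, acute exacerbation and survival. The size is best described by the visit-window column above. Those figures are per endpoint and rest on assumed event rates, a constant hazard, the assumed share followed to Week 56 and the assumed 15% early discontinuers; the documents supply none of these. The higher figures in the other column need every event-free patient to be censored exactly at Week 52, which the protocol's visit windows make unrealistic. The conclusion that the text needs correcting does not depend on the exact probability.

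**What to change.** In SAP 4.4.2.3, end the counting window at *the end of the placebo-controlled period (Week 52)* instead of at the end of study, for all four endpoints, so that only events up to that limit enter the efficacy analysis. Keep the present censoring rules for patients lost earlier. In particular, do not carry a patient forward to a scheduled Week 52 date, which would credit event-free time that was not observed. Report events in Weeks 52 to 56 in the safety summaries, which under SAP 4.6 already cover that period.

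The cost is one sentence and a handful of late events leaving the efficacy analysis: n × p gives about 0.12 (r = 5%, s = 10%) to 1.04 (r = 15%, s = 30%) expected per arm and endpoint, and they add almost nothing to the log-rank test as planned.

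Censoring event-free patients at Week 56 when they are followed that far would also remove the artefact: in the worked arm, S at Day 380 would be 0.870, 0.888 or 0.894 with 10%, 25% or 50% followed. It would keep the late events, but the length of follow-up would still depend on the choice made at Week 52.
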